2.4.5.5.3 NAb

The neutralizing antibody (NAb) assay is based on vWF-platelet interaction. As this assay is not sufficiently drug tolerant to detect NAb under treatment, only pre-dose samples (i.e. baseline visit), recurrence visit day 1 (if applicable) and wash out samples (follow-up samples) will be analyzed. All samples confirmed positive in the ADA assay at these time points will be analyzed in the NAb assay. Samples scoring negative in the NAb assay will be reported as $<\log_{10}(\text{MRD})$ with $\text{MRD} = 2.30$ i.e. $\log_{10}(\text{titer}) < 0.36$. The latter are not included in descriptive statistics on titers. Samples scoring positive will be reported as ≥ 0.36 . These positive samples should be plotted as $\log(\text{MRD})$ equal to 0.36 in the figure.

Subjects will be classified based on their pre-dose status (i.e. baseline visit) and treatment emergent (TE) status. Subject classification based on NAb is as follows:

1. Pre-dose negative,- TE negative: no NAb positive samples
2. Pre-dose negative,- TE positive: ADA or NAb negative at baseline visit and one or more NAb positive samples post-dose
3. Pre-dose positive,- TE negative: NAb positive at baseline visit and all post-dose samples score NAb negative
4. Pre-dose positive,- TE positive: NAb positive at baseline visit and at least 1 NAb positive post-dose sample
5. Missing: Relevant samples are missing.

Subjects with no positive ADA samples will be classified as NAb pre-dose negative, TE negative (data imputation). In listings, samples not evaluated in the NAb assay will be indicated as not analyzed (NA). In graphical presentations, these samples will be presented as negative results.

2.4.5.5.4 NECA (*neutralizing antibody epitope characterization assay; null variant assay; alternative NAb*): *ADA with neutralizing potential*

To detect ADA with potential neutralizing activity under treatment, an alternative NAb assay will be used, consisting of the homogenous bridging ADA assay in which an altered caplacizumab molecule (i.e. caplacizumab with mutated complementary determining region [CDR] regions) is added in excess to capture all non-CDR binding ADA. Consequently, using this assay, only ADA binding to the CDRs of the Nanobody are detected. Those ADA are considered to have neutralizing potential, although clinical relevance (i.e., ability to block binding of von Willebrand factor [vWF]) will be dependent on affinity and titer level and should be related to PK, PD, safety and efficacy read-outs.

All samples confirmed positive in the ADA assay, will be analyzed in this alternative NAb assay. Samples scoring positive in the alternative NAb assay are titrated. The titer per sample is reported as log₁₀ (titer). Samples scoring negative in the alternative NAb assay are not titrated and the respective titer is reported as < log₁₀ (MRD) with MRD = 96, i.e. log₁₀ (titer) < 1.98. The latter are not included in descriptive statistics on titers.

Subjects will be classified based on their pre-dose status (i.e. baseline visit) and treatment emergent status. Subject classification based on alternative NAb assay is as follows:

1. Pre-dose negative, - TE negative: no alternative NAb positive samples
2. Pre-dose negative, - TE positive: ADA or alternative NAb negative at baseline visit and one or more alternative NAb positive samples post-dose.
3. Pre-dose positive, - TE negative: alternative NAb positive at baseline visit and no titer increase post-dose or all samples scoring alternative NAb negative post-dose
4. Pre-dose positive, - TE positive: alternative NAb positive at baseline visit and titer increase post-dose. If a positive pre-dose titer is reported, the titer is considered to be significantly increased post-dose, if the highest post-dose titer compared to the pre-dose titer is higher than the minimum significant ratio [MSR] value: the increase of the log₁₀ titer post versus pre-dose should be > log₁₀ (MSR). The MSR value was determined in Ablynx GLP and is 1.89.
5. Inconclusive: no alternative NAb positive samples and drug is present at levels higher than the drug tolerance characteristics of the assay. Drug tolerance limit is 10µg/mL.
6. Missing: Relevant samples are missing.

Subjects with no positive ADA sample will be classified as “pre-dose negative- TE negative” (#1) in the alternative NAb assay (data imputation). In listings, samples not evaluated in the alternative NAb assay will be indicated as not analyzed (NA). In graphical presentations they will be presented as negative results at the specific sample time points.

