patients in the caplacizuamb treatment group and 18 (9.8%) patients in the abciximab treatment group and were most frequently 'injury, poisoning and procedural complications' and 'cardiac disorders'. By Day 30 there was 1 death in the abciximab group and none in the caplacizumab group. After 1 year of FU, there were 5 deaths in each treatment arm. All but one of the deaths were considered to be unlikely/not related to the study drug. This other death (in the caplacizumab treatment group) was considered possibly related to treatment.

In this Phase II study, treatment-emergent antibodies were detected in 10.9% of the caplacizumab-treated subjects. No neutralizing antibodies were detected.

The PD assessments showed an immediate drop in RICO activity 5 to 10 minutes after the caplacizumab bolus injection. Clinically relevant RICO inhibition (< 20%) was maintained for 24 hours post-bolus in the caplacizumab group which was accompanied by an expected transient and mild decrease in vWF antigen and FVIII activity.

Phase III study

One Phase III study is currently ongoing in the development of caplacizumab for the treatment of acquired TTP:

Study ALX0681-C301 (HERCULES) is a randomized, double blind, placebo-controlled study to evaluate the efficacy and safety of caplacizumab treatment in addition to standard of care treatment (daily PE + corticosteroid treatment) in subjects with an acute episode of acquired TTP. The study will evaluate the efficacy of caplacizumab in more rapidly restoring normal platelet counts and the effect of treatment with caplacizumab on a composite endpoint of TTP-related mortality, prevention of recurrence of the presenting TTP episode and prevention of major thromboembolic events during study drug treatment.

After confirmation of study eligibility and after the start of PE treatment, approximately 92 subjects with a clinical diagnosis of acquired TTP are to be randomized in a ratio of 1:1 to either receive caplacizumab or placebo in addition to standard of care therapy. Subjects are treated for 30 days after stop of daily PE treatment (with a possibility of weekly extensions for a maximum of 4 weeks in case of persistent signs and symptoms of continued underlying disease activity) with a 4 week FU period. Subjects who experience a first exacerbation or a first relapse during treatment extension are to crossover to open-label caplacizumab.

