The visit schedule upon initiation of treatment consists of a recurrence visit at presentation, a visit on Day 3 of treatment with caplacizumab, weekly visits during treatment with caplacizumab (starting 1 day after the last daily PE), and a recurrence FU visit 1 week after the end of treatment with caplacizumab. At these visits, information with regard to the TTP recurrence (presenting symptoms, duration, and outcome) and treatment choice will be collected as will safety information (including AEs, safety laboratory parameters, vital signs and physical examination), and determination of pharmacokinetic [PK], ADA, pharmacodynamic [PD] parameters (vWF:Ag and Ristocetin cofactor activity [RICO]), and disease-related markers (ADAMTS13 activity and Tnl).

In case of recurrent thrombocytopenia requiring re-initiation of daily PE during an ongoing recurrence period (see [Figure 1](#)), a new visit cycle is to be started, with a recurrence visit on the day of the new recurrence followed by all subsequent visits as indicated in [Table 5](#). An i.v. loading dose of caplacizumab needs to be administered prior to re-initiation of PE for the recurrence. All remaining visits of the original schedule are no longer applicable and are not to be performed.

Q6M visits that are scheduled within a recurrence period will not be held as assessments at such visits would be confounded by the concurrent recurrence. Treatment with caplacizumab may not be initiated for subjects who do not fulfil the caplacizumab treatment criteria. Hence, these subjects will be treated with standard of care only. The visit schedule in case of initiation of only standard of care treatment includes a recurrence visit at presentation and a recurrence FU visit at 30 days after end of daily PE (see [Table 6](#) for schedule of assessments).

Figure 1 - Study flow of study ALX0681-C302

M: month; Y : year

Treatment in case of recurrence:

Initiation of treatment with caplacizumab is for subjects with a clinical diagnosis of an episode of recurrent acquired TTP requiring initiation of daily PE treatment and who had a baseline visit.

Treatment with caplacizumab is not permitted for subjects who:

- Are pregnant or intend to get pregnant in the near future
- Have a history of a severe and/or serious hypersensitivity reaction to investigational medicinal product (IMP) in Study ALX0681-C301 or Study ALX0681-C302.

Standard of care treatment (per standard site practice) can include:

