2 STATISTICAL AND ANALYTICAL PROCEDURES

2.1 ANALYSIS ENDPOINTS

2.1.1 Demographic and baseline characteristics

For analysis related to the on-study period, the baseline is defined as the screening/baseline visit.

For analysis related to the recurrence period, the baseline value is defined as the recurrence visit of that recurrence episode.

All baseline parameters are presented along with the on-treatment summary statistics in the sections ([Section 2.4.5](#) and [Section 2.4.4](#)).

Demographic characteristics

Demographic variables are:

- Gender at birth: (Male, Female),
- Race: (not allowed to ask / white / black or African American / Asian / American Indian or Alaska native / native Hawaiian or other Pacific islander / other),
- Age in years at inform consent
- Ethnicity (Hispanic, non-Hispanic),

Medical or surgical history

Medical history includes:

- General medical history
- TTP-related medical history: TTP episodes and major thromboembolic events (e.g., myocardial infarction, cerebrovascular accident, pulmonary embolism, deep venous thrombosis, transient ischemic attack, heart failure, unstable angina, coronary revascularization)
- History of hypersensitivity to IMP in study ALX0681-C301

This information will be coded using version 22.0 of Medical Dictionary for Regulatory Activities (MedDRA).

Vital signs

Vital signs at baseline are weight in kilograms, height, blood pressure and pulse (assessed after 5 min in supine position).

Baseline disease characteristics

Baseline disease characteristics are measured at the recurrence visit. It includes:

- ADAMTS13 activity at admission or baseline: <10% / ≥10%
- Baseline organ damage markers: (LDH, TnI and serum creatinine): ≤ULN / >ULN
- Baseline platelet count.
- Baseline RICO activity, vWF:Ag concentration

Any technical details related to computation, dates, and imputation for missing dates are described in [Section 2.5](#).

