2.4.5.5.2 ADA and mADA analysis

ADA

Immunogenicity samples will be evaluated in a three-tiered homogenous bridging ADA assay (screen/confirmatory/titer tiers). All samples confirmed positive in the ADA assay will be titrated. The log₁₀ (titer) will be reported. The titer represents the last dilution factor of the sample's titration series still scoring positive in the ADA assay.

Samples scoring negative in the ADA assay are not titrated and the respective log₁₀ (titer) is reported as < log₁₀ (Minimal required dilution [MRD]) with MRD = 96, i.e. log₁₀ (titer) < 1.98. The latter are not included in descriptive statistics on titers.

Subjects will be classified as follows based on the ADA assay results:

1. ADA negative: no positive ADA samples at any of the sampling time points
2. ADA positive: positive ADA samples at one or more sampling time points
3. Inconclusive: no positive ADA samples and drug is present at levels higher than the drug tolerance characteristics of the assay. Drug tolerance limit is 10µg/mL.
4. Missing: missing will only be used if samples were taken but no reportable result could be obtained for that subject.

Based on these ADA results, no statement can be made on pre-existing antibody (pre-Ab) positivity pre-dose due the plasma exchange (PE) procedure. During PE (i) pre-Ab present in donor plasma can be transferred to the subject and/or (ii) pre-Ab might be diluted during PE treatment. PE is part of the standard of care and no ADA pre-PE sample will be available to determine the pre-Ab status of the subject.

mADA

All confirmed positive ADA samples will be further evaluated in a mADA assay. This assay employs a modified caplacizumab molecule as detection reagent in the bridging format, ie, caplacizumab-Ala variant. The modification constitutes of a single alanine extension at the C-terminus of caplacizumab. The mADA assay allows detection of drug-induced treatment-emergent (TE) ADA, whereas pre-Ab is not detected. In other words, drug-induced TE ADA will score positive in the mADA assay. All samples confirmed positive in the mADA assay will be titrated and reported as log₁₀ (titer). Samples scoring negative in the mADA assay are not titrated and the respective log₁₀ (titer) is reported as < log₁₀ ([MRD) with MRD = 96, ie, log₁₀ (titer) < 1.98. The latter are not included in descriptive statistics on titers.

Subjects will be classified as follows based on the mADA assay results:

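### A recurrence-visit sample taken during ongoing caplacizumab dosing can be reported as NAb negative, although the SAP says the NAb assay cannot detect NAb under treatment

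*SAP*

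**What the plan says.** - **NAb sampling (SAP 2.4.5.5.3).** The assay is "not sufficiently drug tolerant to detect NAb under treatment, only pre-dose samples (i.e. baseline visit), recurrence visit day 1 (if applicable", and wash-out samples are added. Only ADA-confirmed samples at these visits are assayed. No drug-level condition is attached to the recurrence visit.
- **NAb classes (same section).** The first class reads "Pre-dose negative,- TE negative: no NAb positive samples". The only other residual class is for missing samples.
- **Other assays.** The ADA, mADA and overall lists (SAP 2.4.5.5.2) each have an *Inconclusive* class for when "drug is present at levels higher than the drug tolerance characteristics of the assay". The NECA list (SAP 2.4.5.5.4) has one too: "Inconclusive: no alternative NAb positive samples and drug is present at levels higher than the drug tolerance characteristics of the assay". All four use a limit of 10 µg/mL.
- **Recurrence on treatment (SAP 1.4; Protocol 3.1.1, 3.3.1, 3.4.1.3).** "In case of recurrent thrombocytopenia requiring re-initiation of daily PE during an ongoing recurrence period", "a new visit cycle is to be started, with a recurrence visit on the day of the new recurrence", and the remaining visits of the old cycle are dropped.
- **Baseline (SAP 2.1.1).** "For analysis related to the recurrence period, the baseline value is defined as the recurrence visit of that recurrence episode". RICO and vWF:Ag are named among the values taken there.

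**The concern.** The SAP limits the NAb assay to visits at which it expects no drug, then includes a visit type that the protocol can place in the middle of daily dosing. At such a visit a negative NAb result carries no information, yet the rules count it as a negative. Immunogenicity of repeated treatment is one of the main endpoints (Protocol synopsis), and Protocol 1.2.5 calls the ADA risk of retreatment unknown. With small numbers, one misread subject can change a NAb table, or the platelet-response and vWF:Ag figures that SAP 2.4.5.5.5 splits by NAb category. The same visit also supplies the vWF:Ag baseline for the new episode.

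**Working it through.** **1. The section's own figures.** log10(2.30) = 0.362 (stated 0.36) and log10(96) = 1.982 (stated 1.98). Both reproduce. No drug-tolerance limit is given for the NAb assay.

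**2. Is the sample on drug?** Dosing is daily through PE, for 30 days afterwards, and for up to 28 more days (Protocol 3.1.1). Doses are about 24 h apart (3.3.6). Note f to SAP Table 5 only requires sampling before that visit's PE or dose, so the previous dose is about 24 h old. The only half-life in the documents is 5–36 h, across animal species (Protocol 1.2.3). Treating decay as first-order is a simplification, since the protocol reports non-linear kinetics. The fraction left is 2^(−t/half-life):

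| Time since last dose | half-life 5 h | half-life 36 h |
|---|---|---|
| 24 h (recurrence on daily dosing) | 3.6% | 63% |
| 4 days | <0.1% | 16% |
| 7 days (planned recurrence follow-up visit) | <0.1% | 3.9% |
| 10 days | <0.1% | 1.0% |

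A recurrence during dosing is therefore sampled on drug. One arising from the six-monthly phase, well after any dosing, is not.

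**3. Would the other assays' safeguard catch it?** Assume a plasma volume of 2.5–3.5 L. A 10 mg dose then adds at most 10/3.5 = 2.9 to 10/2.5 = 4.0 µg/mL. With r = 2^(−24/36) = 0.63, the steady-state trough is dose/volume × r/(1 − r), or 4.9–6.8 µg/mL. That is under 10 µg/mL, so on these assumptions the ADA tier can score the sample positive and pass it to the NAb assay, and no *Inconclusive* flag arises elsewhere.

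**4. What the rules then do.** A masked result is reported as below 0.36 and counts towards a negative class. The old cycle's follow-up visit is dropped, so its wash-out sample is lost. The next NAb-eligible samples are the new cycle's follow-up visit, 7 (±1) days after the last dose, and any later six-monthly visits.

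**5. How many samples.** In the Phase II TTP study 3 caplacizumab subjects had an exacerbation: 3/36 = 8.3% (printed as 8.4%), exact 95% CI 1.8–22.5%. NAb is run only on ADA-positive samples, and drug-induced ADA was found in 9%. If the two are independent, 0.083 × 0.09 = 0.0075, about 1 in 130 treated courses. Pre-existing antibodies can also make a sample ADA positive. The documents give no rate for these, so the upper bound at this exacerbation rate is 8.3%, or 1 in 12.

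Illustration: take 92 subjects (the planned size of the parent study, so an upper assumption) and 18–36% with one treated recurrence (Protocol 1.1 and 1.2.4).
- Treated courses: 92 × 0.18 to 92 × 0.361 = 17–33
- On-drug recurrences (× 0.083): 1.4–2.8
- Of these, with drug-induced ADA (× 0.09): 0.12–0.25

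**6. PD baseline.** SAP 2.4 computes change within each analysis period from that period's baseline. Protocol 1.2.3 reports that caplacizumab lowers vWF:Ag, with recovery after stopping. For an on-drug recurrence the baseline and the later weekly samples are pre-dose troughs of one regimen (after 7 doses, 96–100% of steady state for half-lives of 36 to 5 h). The drug-attributable change is therefore about zero. If the on-drug fall were 20–40% (an assumption), recovery at wash-out would read as 0.2/0.8 = +25% to 0.4/0.6 = +67%. The PD change output named in the SAP is the vWF:Ag scatter plot in 2.4.5.5.5. RICO is summarised as actual values and as <20%/≥20% (2.4.6.2).

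**The case against.** The strongest reply is that one masked sample does not classify a subject. A single positive NAb sample after dosing makes the subject treatment-emergent positive, or positive both before and after dosing. The new cycle's follow-up visit and the remaining six-monthly visits all carry an ADA panel. NECA is planned for exactly this situation, runs on every ADA-positive sample, and has a tolerance limit above the troughs estimated here. The individual plots in SAP 2.4.5.5.5 put PK on the same time axis as NAb, so a careful reader could see that drug was present. The study is descriptive throughout.

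All of this stands, and it keeps the point small. It does not remove it. NECA shows neutralising potential only, as 2.4.5.5.4 says itself, so it does not replace the functional result. The NAb table, listing and category-based figures would still report an uninterpretable sample as negative.

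On PD, the reply is largely right. RICO inhibition shows as <20% whatever the baseline. Protocol 1.2.4 calls the fall in vWF antigen transient and mild in the PCI study. PE and the acute episode also move both markers.

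**Conclusion.** The NAb rule contradicts the SAP's own description of the assay for recurrences that start during dosing, or within days of its end. The size is small: about 0.75% of treated courses under independence, and up to 8.3% if all such samples were ADA positive. The true false-negative rate is unknown. The subject's class is wrong only when NAb is present and the later wash-out samples are also negative or missing. The amendment is still worth making, because it is nearly free and corrects a rule that is wrong as written.

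The documents do not support three stronger readings that a reader might infer:
- **That NAb is the likeliest reason for a recurrence on drug.** Protocol 1.2.4 and 1.2.5 link exacerbation and relapse to low ADAMTS13 activity. ADA had no apparent influence on PK or PD in the Phase II TTP study, and no NAb were found in the PCI study.
- **That 1 in 12 courses yields a false negative.** That figure leaves out the ADA filter and the later samples.
- **That PD change generally reads near zero and would pass for loss of effect.** This is confined to the drug-attributable part of the vWF:Ag percentage change. The protocol statement "Clinically relevant RICO inhibition (< 20%) was maintained for 24 hours post-bolus in the caplacizumab group" comes from an i.v. regimen with its last dose about 6 h before the 24 h reading, so it does not give RICO at a daily s.c. trough.

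The PD point also assumes that a new visit cycle counts as a new recurrence episode. SAP 1.4 and Table 1 suggest so, but SAP 2.1.4 leaves it open. The NAb point does not depend on this.

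**What to change.** In SAP 2.4.5.5.3:
- Treat a recurrence-visit NAb result as evaluable only if the paired PK sample is BQL, or below a NAb drug-tolerance limit if the SAP states one. Otherwise report a negative at that visit as not evaluable, in listings and plots as well, and keep any positive.
- State the rule for visits without a PK sample. SAP Table 6 schedules none when caplacizumab is not started, so the dosing record has to stand in.
- Add a subject class *Inconclusive* for subjects with no NAb-positive sample and no evaluable drug-free post-dose sample, and read it alongside NECA.

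For PD, flag episodes that start on drug and present their vWF:Ag percentage change separately, or show actual values. Carrying back an older baseline is not recommended, because it brings in the disease state of an earlier acute presentation. RICO as actual values and <20%/≥20% needs no change.

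The cost is SAP wording and some programming. For recurrences treated with caplacizumab the PK sample is already scheduled at the same visit. The downside is that a very small number of results move from negative to not evaluable or inconclusive.

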2.4.4.8 Multiplicity issues

There are no multiplicity issues because no formal statistical test will be performed.

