2.4.5.5.1 Available data

The available parameters per sample are:

- Anti-drug antibody (ADA) log₁₀(titer) (no data imputation). Titers <log₁₀ are considered ADA negative.
- Modified anti-drug antibody (mADA) assay log₁₀(titer) (for subset of subjects only, no data imputation)
- Neutralizing antibody (NAb) log₁₀(titer) (for subset of samples only, data imputation required for ADA negative samples)
- NECA log₁₀(titer) (for subset of samples only, data imputation required for ADA negative samples)

Based on the above listed data per subject, a subject classification will be attributed for each assay, resulting in the following reported data per subject:

- ADA subject classification (all subjects)
- mADA subject classification (for subset of subjects)
- Overall subject classification (based on ADA and mADA analysis)
- NAb subject classification (all subjects)
- NECA subject classification (all subjects)

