- The number and percentage of subjects classified as pre-Ab negative, pre-Ab positive, drug-induced TE negative and drug-induced TE positive

NAb assay result

The number and percentage of subjects will be summarized using following categorization. This analysis will be performed on subset of the population, consisting of subjects who were classified as ADA positive based on ADA data.

- Each NAb subject category
- Classified as pre-dose negative, pre-dose positive, TE negative and TE positive

Alternative NAb (null variant) assay result

The number and percentage of subjects will be summarized using following categorization.

- Each alternative NAb subject category
- Classified as pre-dose negative, pre-dose positive, TE negative and TE positive

Incidence of positive alternative NAb samples by visit.

Spaghetti plot of alternative NAb log₁₀ (titer) vs. time. Negative values for alternative NAb (reported as log₁₀ (titer) < 1.98) will be visualized on the graphs as 1.80 (arbitrarily chosen) to allow plotting. The MRD (or sensitivity of the assay) will be visualized as horizontal line at log₁₀ (titer) = 1.98.

Individual line plots of ADA log₁₀ (titer), mADA log₁₀ (titer), NAb log₁₀ (titer), alternative NAb log₁₀ (titer), PK, RICO activity, vWF:Ag concentration, over time with indication of PE treatment days and treatment with rituximab. PE and rituximab treatment days should be visualized on the plot. For ADA, mADA, and alternative NAb titer plotting, negative values (reported as log₁₀ (titer) < 1.98) will be visualized on the graphs as 1.80 (arbitrarily chosen) to allow plotting. The MRD (or sensitivity of the assay) will be visualized as horizontal line at log₁₀ (titer) = 1.98. Negative values for NAb assay (reported as log₁₀ (titer) < 0.36) will be visualized on the graphs as 0.20. The MRD of the NAb assay will be visualized as a horizontal line at log₁₀ (titer) = 0.36. Different responses can be plotted against separate Y-axes above each other, but scale of time-axis should be identical for each plotted response.

Listing of all immunogenicity parameters (ADA log₁₀ (titer), mADA log₁₀(titer), NAb result log₁₀(titer), alternative NAb result log₁₀(titer)) at each time point.

Listing of subject classification based on ADA assay, mADA assay, overall subject classification (based on ADA and mADA assay results) and listing of subject classification based on NAb assay and alternative NAb assay.

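### The SAP's figure rule draws ADA-positive on-treatment samples as NAb negative in the individual line plots, although the NAb assay is never run on them

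*SAP*

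**What the plan says.** SAP 2.4.5.5.3 gives the reason for restricting the NAb assay and names the eligible time points: "As this assay is not sufficiently drug tolerant to detect NAb under treatment, only pre-dose samples" (the baseline visit), "recurrence visit day 1 (if applicable) and wash out samples (follow-up samples) will be analyzed". Within those time points, ADA status decides what is run: "All samples confirmed positive in the ADA assay at these time points will be analyzed in the NAb assay".

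Two display rules for samples without a NAb result follow. The first covers listings: "In listings, samples not evaluated in the NAb assay will be indicated as not analyzed (NA". The next sentence covers figures: "In graphical presentations, these samples will be presented as negative results".

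Two other places bear on this:
- SAP 2.4.5.5.1, describing the NAb data: "for subset of samples only, data imputation required for ADA negative samples".
- SAP 2.4.5.5.5, on the individual line plots, which show ADA, mADA, NAb, alternative NAb, PK, RICO and vWF:Ag for one subject against a common time scale: "Negative values for NAb assay (reported as log₁₀ (titer) < 0.36) will be visualized on the graphs as 0.20". The NAb threshold line is drawn at 0.36, and 2.4.5.5.3 plots NAb positives at that value.

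**The concern.** A sample can lack a NAb result for two different reasons. It may be ADA negative, in which case showing it as NAb negative is a fair imputation. Or it may be ADA positive but taken on drug, in which case the SAP itself says the assay could not have given a usable answer. The figure rule treats both alike, so an absent result in the second group becomes a plotted negative that looks the same as a tested one.

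The individual line plots set a subject's antibody traces beside drug concentration and RICO. If a subject is ADA positive and loses drug effect during treatment, the NAb trace would read negative at those very visits, although nothing was measured. Immunogenicity of (repeated) treatment is among the main endpoints in the protocol synopsis, and protocol section 1.2.5 says it is not yet known whether retreatment carries a risk of inducing ADA. A reader will therefore look to these plots for an answer.

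**Working it through.** **1. The plan's own threshold.** SAP 2.4.5.5.3 gives a NAb minimum required dilution of 2.30. log10(2.30) = 0.3617, which rounds to the stated 0.36. The value for the other three assays also reproduces: log10(96) = 1.982, stated as 1.98. A point at 0.20 therefore lies below the NAb line and reads as negative.

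**2. The rules applied to each kind of sample.**

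| Sample | Run in NAb assay? | Listing | Figure | Covered by the imputation in 2.4.5.5.1? |
|---|---|---|---|---|
| ADA negative, any visit | No | NA | 0.20 | Yes |
| ADA positive; baseline, recurrence visit or wash-out | Yes | Result | 0.20 or 0.36, as tested | Not needed |
| ADA positive; Day 3 or a post-daily PE visit on treatment | No | NA | 0.20 | No |

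The third row is the defect. The value 0.20 follows from two rules together: untested samples are shown as negative (2.4.5.5.3), and negatives are plotted at 0.20 (2.4.5.5.5).

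**3. How many visits are exposed.** Protocol Table 2 schedules an ADA sample at every visit of a caplacizumab-treated recurrence.
- No extension: recurrence visit, treatment Day 3, post-daily PE Days 1, 8, 15, 22 and 29, and the recurrence FU visit. Total 1 + 1 + 5 + 1 = 8.
- Full 4-week extension: the weekly visits continue at Days 36, 43, 50 and 57. Total 8 + 4 = 12.
- NAb-eligible in either case: the recurrence visit and the recurrence FU visit, taking the latter as the wash-out sample. Total 2.
- Not eligible: 8 − 2 = 6, and 6/8 = 75%; with full extension 12 − 2 = 10, and 10/12 = 83%.

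These count visits, not misdrawn points. The number of misdrawn points is the number of ADA-positive samples among the 6 to 10, from 0 up to all of them.

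**4. Sensitivity to the denominator.** Protocol Table 1 adds seven twice-yearly ADA samples (baseline to 36 months). Suppose all seven appear in the same plot, none is skipped, and all count as baseline or follow-up samples for the NAb assay. One treated recurrence then gives 6/(8 + 7) = 6/15 = 40%, or 10/(12 + 7) = 10/19 = 53% with full extension.

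**5. Which outputs use the rule.**
- Listings show NA, which is correct.
- NAb subject classification and its tables use assay results and a separate imputation for subjects with no ADA-positive sample. They do not read plotted points.
- No NAb spaghetti plot and no NAb incidence by visit are planned; 2.4.5.5.5 plans both for the alternative NAb assay.
- The scatter plots of drug concentration, vWF:Ag change and RICO, and the Kaplan-Meier plot of platelet response, are drawn by subject category.
- The NAb trace in the individual line plots is the one output affected.

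**The case against.** The strongest argument is that the sentence was never meant to reach ADA-positive samples. It closes a paragraph that opens with the imputation for subjects who have no positive ADA sample. SAP 2.4.5.5.1 ties NAb imputation to ADA-negative samples. SAP 2.4.5.5.4 repeats nearly the same wording for NECA, where every ADA-positive sample is run, so unevaluated samples there are in principle ADA negative. That may well explain how the wording arose. It does not fit the text: the samples in the figure rule are those named in the sentence just before it, all samples not evaluated in the NAb assay, and no ADA condition is attached. A programmer following it would plot on-treatment ADA positives at 0.20.

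The second argument is that NECA fills the gap. The SAP introduces it to detect potentially neutralising antibody under treatment, runs it on all ADA-positive samples, and plots it in the same individual figure. This stands, and it makes a false conclusion considerably less likely. It does not make the NAb trace right. NECA measures binding to the CDRs, not function, so a NECA positive beside an invented NAb negative could be read as a functional refutation.

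The third argument concerns size, and it also stands. Treatment-emergent ADA occurred in 9% of caplacizumab-treated subjects in the earlier phase II TTP study (protocol 1.2.4), so few subjects may be affected. That figure is not a ceiling, however: under SAP 2.4.5.5.2 pre-existing antibody, including antibody transferred in donor plasma, also makes a sample ADA positive.

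A reader might go further and infer that 75% to 83% of NAb points are false, that NAb rates or categories are biased, or that neutralisation under treatment is not assessed at all. The documents support none of these. The percentages count ineligible visits, the tables do not use plotted values, and NECA covers the on-treatment samples.

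**Conclusion.** Wrong as written, but a minor display error. The figure rule gives untested ADA-positive on-treatment samples the appearance of tested NAb negatives, against the SAP's own listing rule and its own description of the imputation. At most 6 of 8 scheduled ADA visits in a treated recurrence are exposed, or 10 of 12 with full extension. The actual number misdrawn depends on ADA positivity on treatment, which the documents do not report.

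It would be too strong to say that every ADA-positive sample taken on drug is misdrawn. A new recurrence during an ongoing treated episode starts a new visit cycle, and its recurrence-visit sample is NAb-eligible although drug may still be present.

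The conclusion rests on reading the figure rule by its grammatical antecedent and on taking the recurrence FU visit as wash-out. The study is descriptive ("There are no multiplicity issues because no formal statistical test will be performed"), so no inference depends on the plots. What is at stake is how a reader interprets individual subjects' traces.

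**What to change.** In SAP 2.4.5.5.3, limit the figure rule: show as NAb negative only samples that tested negative in the NAb assay or were ADA negative. Show ADA-positive samples not run in the NAb assay as a gap or with a distinct not-analyzed symbol, and do not join the line across them. A footnote to the individual line plots can direct the reader to the NECA trace for on-treatment samples.

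The cost is one SAP sentence and one plotting condition. No new data or assays are needed, and no table or listing changes.
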